## **2.7.2 Asthma control questionnaire (ACQ)**

Results for ACQ-7 at day 30, obtained from MMRM for the key secondary endpoint ACQ-7 at day 84, will be displayed.

Change from baseline in the ACQ-7 will be also analyzed using the same MMRM model.

The proportion of patients who achieve an improvement of at least 0.5 in ACQ-7 (i.e. decrease of ACQ-7 score of at least 0.5 from Baseline) at post-baseline visits will be analyzed using a logistic regression model. First missing ACQ-7 values will be imputed using a regression based Multiple Imputation (MI) method under missing at random (MAR) assumption, based on continuous ACQ values. Then continuous ACQ values will be converted into binomial responses and generalized estimating equation (GEE) method will be used to analyze the datasets and then the results from GEE method will be combined for the inference. The GEE model will include terms for treatment, age (12 to 17 or  $\geq 18$  years), region, visit, and treatment-by-visit interaction as fixed effects, and Baseline ACQ-7, Baseline-by-visit interaction, FEV1 prior to inhalation and FEV1 within 15 to 30 min post inhalation of salbutamol/albuterol (components of SABA reversibility) as covariates. The estimated adjusted odds ratio will be displayed along with the associated 95% (2 -sided) confidence interval and p-value.

Additionally, the number of patients will be summarized by response relative to baseline ACQ-7 with the following categories: Response (decrease of  $\geq 0.5$  units in ACQ-7), No change ( $-0.5 < \text{change in ACQ-7} < 0.5$ ), Worsening (increase of  $\geq 0.5$  units in ACQ-7), Net response (response – worsening) and Total.

In addition to ACQ-7, average of first 5 questions in ACQ (ACQ-5) will be calculated and all the analyses described for ACQ-7 will be repeated for ACQ-5.

### **2.7.3 Rescue medication**

The number of puffs of the rescue medication use in the last 12-hour is recorded twice daily (morning/evening) by the patient in his/her e-Diary. For rescue medication use, the baseline values are defined as the average from all non-missing records taken over the last 21 days in the run-in period between run-in Visit 101 and up to one day before first dose of study treatment. Missing diary data will not be imputed.

If for the value over the whole day (24 hours) the number of puffs is missing for part of the day (either day-time or night-time) then a half day will be used in the denominator to calculate the average value. Any values  $> 30$  for the number of puffs of rescue medication in a 12 hour period will be set to missing. These high numbers are not realistic and could impact the analyses. If a patient has less than 7 days with non-missing data, then the baseline value will be set to missing.

Post-baseline measurements start with the morning recordings at Day 2 and end with the evening recordings one day after the last evening dose. Summary data (i.e., mean values and percentage of days with) will be calculated for 4-weekly intervals (defined as 28 days), and for Weeks 1 – 12 (defined as the whole treatment period up to Visit 204, Day 85). Similar calculations as for baseline diary data will be done. If there will be less than 14 days with data in a 4-week period, then the data should collapse with the previous 4-week period. For Weeks 1 – 12, summary values will only be calculated if a patient has at least 30% of their diary days and at least 20 diary days with evaluable data for that variable.

The mean daily number of puffs of rescue medication use over the 12 weeks of treatment will be summarized by treatment. The change from Baseline in the mean daily number of puffs of rescue medication use will be analyzed using an ANCOVA model. The model will contain treatment, age (12 to 17, or  $\geq 18$ ), region as fixed effect factors with center nested within region as a random effect and baseline rescue medication use, FEV1 prior to inhalation and FEV1 within 15 to 30 min post inhalation of salbutamol/albuterol (components of SABA reversibility) as covariates. No imputation will be done for missing data. The adjusted mean (LS mean) treatment difference along with the corresponding two-sided 95% confidence interval and corresponding p-value will be presented. This analysis will be performed for morning (nighttime), evening (daytime), and daily (average of nighttime and daytime) rescue medication use.

The percentage of ‘rescue medication free days’ (defined from diary data as any day where the patient did not use any puffs of rescue medication during daytime and nighttime) will be summarized by treatment and analyzed the same way as described for the number of puffs of

the rescue medication use with baseline percentage of 'rescue medication free days' as a covariate instead of baseline rescue medication use.

In addition, the mean number of puffs of rescue medication per day, in the morning and in the evening and the percentage of 'days with no rescue use' will be summarized by 4 weekly (28 days) intervals and the change from baseline in mean number of puffs of rescue medication will be analyzed using a similar MMRM as specified for the primary analysis with the baseline FEV1 value replaced with the appropriate baseline rescue medication use. In case of non-convergence or evidence of highly skewed data, non-parametric tests such as Wilcoxon Rank Sum Test will be explored.

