#### Lung function:

- Trough FEV1 at Day 2 of treatment period (defined as the mean of 23 h15 min and 23 h 45min FEV1 values post dose of Day 1.)
- Pre-dose FEV1 (defined as the mean of -45 min and -15 min FEV1 values pre-evening dose) at 4 weeks
- Forced Vital Capacity (FVC) and Forced Expiratory Flow between 25% and 75% of FVC (FEF25-75) over 12 weeks
- Morning and Evening Peak Expiratory Flow Rate (PEF) over 4 and 12 weeks of treatment.

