#### **2.7.4 Peak Expiratory Flow Rate (PEF)**

All the patients are instructed to record PEF twice daily using an electronic Peak Flow Meter device, once in the morning and once approximately 12 hours later in the evening (prior to evening dose), from Run in visit 101 and throughout the study. PEF (liters/min) will be averaged separately for morning and evening values with means over the 12 weeks treatment phase and the 3 weeks Baseline Run-in phase.

Baseline values are defined similarly as rescue medication in Section 2.7.3

For post-baseline measurements, similar procedure will be followed, as mentioned for rescue medication use.

Mean morning/evening PEF over 12 weeks of treatment phase will be summarized by treatment. The between-treatment difference of the change from baseline in mean morning/evening PEF will be analyzed using the same model as specified for rescue medication data except that baseline rescue medication use will be replaced with baseline morning/evening PEF as the covariate. LS means and associated 95% confidence intervals will be presented for treatments and the treatment difference.

In addition, the mean morning/evening PEF will be summarized by 4 weekly intervals and the change from baseline in mean morning/evening PEF will be analysed using a similar MMRM as specified for the primary analysis with baseline FEV1 value replaced with the appropriate baseline PEF.

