Baseline values are defined similarly as rescue medication in Section 2.7.3. Additionally, the baseline total daily symptom score will be obtained in the first step by adding the nighttime symptom score, the morning score, and the mean daytime symptom score for each single day. In the second step, these daily symptom scores will be averaged over the days of the run-in period with non-missing data. The score is in the range from 0 to 12. For the derivation of the total daily symptom score, all 3 scores have to be available at that day. Otherwise a total daily symptom score will not be calculated for that day. If a patient has less than 7 days with non-missing data, then the baseline value will be set to missing.

For post-baseline measurements, similar procedure will be followed, as mentioned for rescue medication use.

Daily scores will be averaged for each patient over the days of the run-in period (which will be used as the baseline value), 12 weeks double-blind period, and over 4 weekly intervals (from Weeks 1-4 up to Weeks 9-12). Days with no daytime symptoms, nights with no night time awakenings, mornings with no symptoms on awakening and days with no asthma symptoms will be expressed in percentage of days with data during the respective periods. The same periods as for average scores will be analyzed for percentage of days. In case of non-convergence or evidence of highly skewed data, non-parametric tests such as Wilcoxon Rank Sum Test will be explored. For post baseline periods only the days on double-blind treatment will be considered. ANCOVA and MMRM will be performed on changes from baseline similar to the analysis of PEF with the appropriate baseline symptom score value as a covariate.

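### Merging a sparse 4-week diary interval into the one before it can put Weeks 5-8 days into the Weeks 1-4 PEF value; the effect is small and one SAP sentence removes it

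*SAP*

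**What the plan says.** SAP section 2.7.3 (Rescue medication) sets out how diary data are reduced to interval summaries. On timing: "Post-baseline measurements start with the morning recordings at Day 2 and end with the evening recordings one day after the last evening dose". Summaries are formed over 28-day intervals and over Weeks 1-12. For a thinly recorded interval the rule is: "If there will be less than 14 days with data in a 4-week period, then the data should collapse with the previous 4-week period".

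The rule reaches PEF through section 2.7.4: "For post-baseline measurements, similar procedure will be followed, as mentioned for rescue medication use". Section 2.7.5 says the same for the symptom scores and names the intervals as running from Weeks 1-4 to Weeks 9-12. The interval values for PEF are analysed as change from baseline with an MMRM modelled on the primary analysis.

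The lung-function objectives in SAP section 1.2.3 and protocol section 2.3 include "Morning and Evening Peak Expiratory Flow Rate (PEF) over 4 and 12 weeks of treatment". Protocol sections 9.6.1.3 to 9.6.1.5 describe the 4-weekly summaries but give no minimum number of days and no merging rule.

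**The concern.** A repeated-measures model with interval as the time factor takes each value to describe its own interval. The merging rule breaks that link for some patients. When Weeks 5-8 is sparse, its days move back into Weeks 1-4. That patient's Weeks 1-4 value then covers up to 41 recorded days, against at most 28 in other patients, and the Weeks 5-8 value disappears. The MMRM could have accepted the Weeks 5-8 value as observed or treated it as missing at random. A sparse Weeks 9-12 does the same to Weeks 5-8.

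What is at stake is the timing of a listed secondary endpoint, PEF over 4 weeks, and of the supporting 4-weekly rescue and symptom results. The rule also differs from its neighbours in section 2.7.3. There, a baseline with under 7 days is set to missing, and a Weeks 1-12 value is not calculated below 30% of diary days or below 20 days. Only the interval rule moves data from one period to another.

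**Working it through.** The plan gives no figure for this rule, so there is none to reproduce. The check is a count of days.

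**Inputs from the documents**
- First post-baseline diary day: Day 2 (SAP 2.7.3).
- Interval length: 28 days (SAP 2.7.3).
- Merging threshold: under 14 days with data, so at most 13 days are moved from one interval (SAP 2.7.3).
- Sample size 750 and dropout 10% (SAP section 3).

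**Intervals.** Starting on Day 2 in blocks of 28: Days 2-29, 30-57 and 58-85. The total is 84 days, ending on Day 85 as section 2.7.3 states for Weeks 1-12.

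**One patient.** Share of later data in the merged Weeks 1-4 value = late days / (early days + late days).
- Full first interval, 1 late day: 1/29 = 3.4%.
- Full first interval, 13 late days: 13/41 = 31.7%.
- 14 early days, 13 late days: 13/27 = 48.1%.

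These assume a single merge. The SAP does not say whether merging is chained when Weeks 5-8 and Weeks 9-12 are both sparse. If it were, 26 late days could enter: 26/54 = 48.1% with a full first interval, or 26/40 = 65.0% with 14 early days.

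**Whole trial.** Assumptions: last diary days of dropouts are uniform over Days 2-85, and diaries are complete until then. A dropout is merged into Weeks 1-4 if the last diary day falls on Days 30-42, which is 13 of 84 days.
- Patients merged = 750 x dropout x 13/84. At 5%, 10% and 15% dropout: 5.8, 11.6 and 17.4.
- Average late share among them = (1/13) x sum of k/(28+k) for k = 1 to 13 = 0.191.
- Average later-data weight over all patients = dropout x (13/84) x 0.191. At 5%, 10% and 15%: 0.15%, 0.30% and 0.44%.

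**In PEF units.** The documents give no size for a late fall in PEF, so 10 to 50 L/min is assumed.
- One patient at the 31.7% share: 3.2 to 15.9 L/min.
- Mean over all patients at 0.30%: 0.03 to 0.15 L/min.
- If all 12 merged patients were in one arm of 375: 12/375 x 0.19 x (10 to 50) = 0.06 to 0.30 L/min on that arm's mean.

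**The case against.** The merging is pre-specified, applies identically to both arms, and keeps on-treatment days that would otherwise drop out of the interval results. The main PEF analysis is the ANCOVA on the 12-week mean; the 4-weekly MMRM is additional. PEF lies outside the hierarchical test, so no controlled claim depends on it. Section 2.7.4 asks for a similar procedure, not an identical one, and nowhere states that the 4-week PEF endpoint is the Weeks 1-4 interval. All of this stands and limits the importance of the point. It does not remove the mis-timing. The cross-reference gives no exception for PEF, and no other 4-week PEF analysis is described.

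A reader might infer two stronger points that the documents do not support.

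- **That a sparse Weeks 1-4 would be merged with the run-in, mixing treatment days with baseline.** The rule points to a previous 4-week period. The run-in baseline is "the average from all non-missing records taken over the last 21 days in the run-in period", so it is not one. Post-baseline data start on Day 2, and for symptoms section 2.7.5 adds: "For post baseline periods only the days on double-blind treatment will be considered". Just before the merging rule, section 2.7.3 also says that interval values are calculated in the manner of the baseline values. That plausibly brings in the 7-day minimum for Weeks 1-4. What is missing is an explicit statement.
- **That the misplaced days belong mainly to patients who worsen and drop out, and so differ by arm.** This is possible but not shown. The trigger is days with data, so diary gaps in patients who complete treatment set it off too, and the documents give no rate for either cause by arm.

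**Conclusion.** The point holds as a minor defect in a stated rule. As written, SAP section 2.7.3 can place Weeks 5-8 diary days in the Weeks 1-4 value and lose the Weeks 5-8 value, in an analysis that treats the intervals as distinct. The 32% and 48% shares are maxima for a single patient and should not be read as trial-level effects. With 10% dropout and uniform timing, about 12 of 750 patients are affected and the average later-data weight is about 0.3%. The true figure would be higher by an unknown amount if completers have long diary gaps. The Weeks 1-12 summaries have their own minimum-data rule and are untouched, as are the primary endpoint, the key secondary endpoint and the sample size. For a sparse Weeks 1-4 the plan lacks a detail; it does not call for contamination with baseline.

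**What to change.** Delete the merging sentence from SAP section 2.7.3. In its place, state that each 4-week value uses only the days in that interval, that it is set to missing below a stated minimum, and that the MMRM handles the missing value. State that the rule covers all three intervals, including Weeks 1-4, and applies to rescue use, PEF and symptoms. The share of later data in Weeks 1-4 then becomes 0%.

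Either minimum already in the section would serve. The 7-day baseline minimum was set for a 21-day window (7/21 = 33%) and is looser on 28 days (7/28 = 25%). The existing 14 days is 14/28 = 50%. Under the dropout assumptions above (75 dropouts), a 7-day minimum keeps a Weeks 5-8 value for about 75 x 7/84 = 6 of the 12 affected patients and leaves it missing for about 75 x 6/84 = 5 (unrounded, 6.25 and 5.36 sum to 11.6). A 14-day minimum leaves it missing for all 12.

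The cost is one edited paragraph before database lock. The downside is a few interval means that rest on 7 to 13 days and are noisier, or that are missing.

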#### **2.7.4 Peak Expiratory Flow Rate (PEF)**

All the patients are instructed to record PEF twice daily using an electronic Peak Flow Meter device, once in the morning and once approximately 12 hours later in the evening (prior to evening dose), from Run in visit 101 and throughout the study. PEF (liters/min) will be averaged separately for morning and evening values with means over the 12 weeks treatment phase and the 3 weeks Baseline Run-in phase.

Baseline values are defined similarly as rescue medication in Section 2.7.3

For post-baseline measurements, similar procedure will be followed, as mentioned for rescue medication use.

Mean morning/evening PEF over 12 weeks of treatment phase will be summarized by treatment. The between-treatment difference of the change from baseline in mean morning/evening PEF will be analyzed using the same model as specified for rescue medication data except that baseline rescue medication use will be replaced with baseline morning/evening PEF as the covariate. LS means and associated 95% confidence intervals will be presented for treatments and the treatment difference.

In addition, the mean morning/evening PEF will be summarized by 4 weekly intervals and the change from baseline in mean morning/evening PEF will be analysed using a similar MMRM as specified for the primary analysis with baseline FEV1 value replaced with the appropriate baseline PEF.

#### **2.7.5 Asthma symptoms based on e-Diary**

The night-time symptom score consists of one question 'How did you sleep last night?' which has to be answered with scores from 0 = 'I did not wake up because of any breathing problems.' up to 4 = 'I had difficulty sleeping because of my breathing problems even though I used my rescue medication.' The morning score consists of the question 'Did you have asthma symptoms upon awakening in the morning?' which has to be answered with scores from 0 = 'None' up to 4 = 'Very Severe'. There are 5 questions including the today's severity of shortness of breath,

wheeze, cough, and chest tightness during the past 12 hours, and 'Did your respiratory symptoms stop you from performing your usual daily activities?' which are part of the daytime symptom score. All have to be answered with a score from 0 = 'None / Not at all' up to 4 = 'Very Severe / Completely'.

Daily e-Diary recordings will be used to derive:

- the mean daytime asthma symptom score i.e., the mean score over the 5 evening questions with respect to shortness of breath, wheeze, cough, chest tightness, and 'Did your respiratory symptoms stop you from performing your usual daily activities?', each with scores from 0 (no problems) to 4 (very severe problems)
- the total daily symptom score, defined as the sum of the nighttime score ('How did you sleep last night?' with scores from 0 - 4), the morning awakening score ('Did you have asthma symptoms upon awakening in the morning?' with scores from 0 - 4) and the mean daytime asthma symptom score. The sum will be in the range of 0 – 12.
- day with no daytime symptoms, i.e., all 5 evening questions must have a score = 0.
- night with no night-time awakenings, i.e., the question 'How did you sleep last night?' must be answered with 'I did not wake up because of any breathing problems'.
- morning with no symptoms on awakening, i.e., the question 'Did you have asthma symptoms upon awakening in the morning?' to be answered with 'None'.
- asthma symptoms free days, i.e., days with no daytime symptoms and no night-time awakenings and no symptoms on awakening.

Baseline values are defined similarly as rescue medication in Section 2.7.3. Additionally, the baseline total daily symptom score will be obtained in the first step by adding the nighttime symptom score, the morning score, and the mean daytime symptom score for each single day. In the second step, these daily symptom scores will be averaged over the days of the run-in period with non-missing data. The score is in the range from 0 to 12. For the derivation of the total daily symptom score, all 3 scores have to be available at that day. Otherwise a total daily symptom score will not be calculated for that day. If a patient has less than 7 days with non-missing data, then the baseline value will be set to missing.

For post-baseline measurements, similar procedure will be followed, as mentioned for rescue medication use.

Daily scores will be averaged for each patient over the days of the run-in period (which will be used as the baseline value), 12 weeks double-blind period, and over 4 weekly intervals (from Weeks 1-4 up to Weeks 9-12). Days with no daytime symptoms, nights with no night time awakenings, mornings with no symptoms on awakening and days with no asthma symptoms will be expressed in percentage of days with data during the respective periods. The same periods as for average scores will be analyzed for percentage of days. In case of non-convergence or evidence of highly skewed data, non-parametric tests such as Wilcoxon Rank Sum Test will be explored. For post baseline periods only the days on double-blind treatment will be considered. ANCOVA and MMRM will be performed on changes from baseline similar to the analysis of PEF with the appropriate baseline symptom score value as a covariate.

## 2.7.6 Asthma Exacerbations

All analyses will base on data as reported on the "Asthma Exacerbation Episodes" eCRF. The following asthma exacerbation-related parameters will be summarized considering the whole 12 weeks of double-blind treatment. The analysis will be performed by exacerbation category wherever specified. The exacerbation categories are: All (mild, moderate, severe) , and the combination of moderate or severe. The data for categories mild, moderate and severe will be collected as a part of Asthma Exacerbation Episode CRF and an additional category moderate or severe will be added for analysis.

- Time to first asthma exacerbation by exacerbation category
- The annual rate of asthma exacerbations by exacerbation category

In patients with multiple exacerbations, if the start date of an exacerbation was less than 7 days after the end date of a previous episode, then this will be assumed to be one continuous exacerbation with the start date taken from the first episode and the end date from the second or last episode. The worst severity of these episodes will be taken as the severity of the collapsed exacerbation. Collapsing of exacerbation episodes will only be done for efficacy analyses but not for safety analyses of adverse events which includes asthma exacerbations.

Asthma exacerbations starting after the first dose and not later than one day after the date of last dose will be included in the analyses of efficacy.

Time-to-event variables will be analyzed using a Cox regression model stratified by age (12 to 17 or  $\geq 18$ ). The model will include treatment, region and history of asthma exacerbation in the 12 months prior to screening (Yes, No) as fixed-effect factors, and FEV1 prior to inhalation and FEV1 within 15 to 30 min post inhalation of salbutamol/albuterol (components of SABA reversibility) as covariates. The estimated adjusted hazard ratio for QMF149 over MF will be displayed along with the associated two-sided 95% confidence interval and corresponding p-value. Kaplan-Meier analysis stratified by treatment group will be also presented and displayed graphically. Patients without any asthma exacerbation will be censored at the earliest date of (last dose of study treatment + 1, death, last visit).

The annual rate of asthma exacerbations will be analyzed using a generalized linear model assuming the negative binomial distribution including treatment, age (12 to 17 or  $\geq 18$ ), and region and history of asthma exacerbation in the 12 months prior to screening (Yes, No) as fixed-effect factors, and FEV1 prior to inhalation and FEV1 within 15 to 30 min post inhalation of salbutamol/albuterol (components of SABA reversibility) as covariates. The log exposure in years will be included as an offset variable in the model. The estimated rate ratio along with two-sided 95% interval and corresponding p-value will be provided.

study treatment

